This assessment visit will last approximately 8 hours, including time for rest and meals, and may be performed within one day or over the course of several days within a 4 week period. Upon completion of all baseline assessments, patients will be block randomized to one of three groups: 1) a waitlist control, 2) an exercise intervention consisting of exercise at vigorous intensity (Aerobic exercise training group, AET), or 3) an exercise intervention consisting of exercise at moderate intensity (Rapid resistive exercise training group, RET). Both training interventions will be performed 3 times a week for 12 weeks, with a session duration of approximately 1 hour. After 12 weeks, all patients will repeat the same assessments performed at baseline (3 month follow-up). Patients in the control group will then be randomized to either AET or RET, while patients in the exercise training groups will cease their formal supervised exercise training regimen. All patients will return after 12 weeks to perform their final assessment visit (6 month follow-up).

All assessments and training interventions are outpatient visits and will occur at the NIH Clinical Center in the Rehabilitation Medicine Department.

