Subjects randomized to the wait-list control will be further randomized to either AET or RET after Assessment Visit 2. In the first 3 months, subjects in the wait-list control will receive no exercise training; however they will be contacted monthly to ensure compliance and to maintain contact (Appendix 10). For subjects initially randomized to either AET or RET, they will no longer follow a formal exercise intervention at NIH following Assessment Visit 2. However, they will be contacted monthly for the next 3 months and asked about their weekly physical activities (Appendix 10).

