### 4.5 Relationship to other protocols

Potential participants do not have to enroll or participate in any other protocol in order to participate in this study.

This study is related to a number of other protocols and projects. The Center for Neuroscience and Regenerative Medicine (CNRM) is a collaborative intramural federal program involving the United States Department of Defense (DoD) and the National Institutes of Health (NIH). It joins clinicians and scientists across disciplines to catalyze innovative approaches to traumatic brain injury (TBI) research.

The Uniformed Services University of Health Sciences (USUHS) heads the operation of the CNRM (www.usuhs.mil/cnrm).

CNRM initially provided Henry Jackson Foundation staff and equipment to NIH through a CRADA. These staff included several providers who perform the assessment instruments. All providers are credentialed at the Clinical Center for work at NIH.

The CNRM Informatics Core was created to store all imaging and clinical data from CNRM-related protocols. All clinical data will be coded and have personally identifying material removed prior to transfer to CNRM.

Research data from neuropsychological assessments, balancing and imaging performed within the past 3 months under other CNRM studies may be included as baseline assessments in this study. This is to avoid patient burden and practice effects. Research data from the same subject may also be shared directly with CNRM investigators in protocol 10-CC-0118 (Long-term Clinical Correlates of TBI: Imaging, Biomarkers and Clinical Phenotyping Parameters) and 11-N-0084 (Evaluation and Diagnosis of Potential Research Subjects with Traumatic Brain Injury).

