# 9. Statistical Analysis

### 9.1 Analysis of data

The primary analysis is a mixed model (with time as the within-subject factor and exercise group as the between subject factor) analysis of variance (ANOVA) which will be used to determine significant differences in the primary (ANOVA) and secondary outcome variables (MANOVA by outcome category – i.e. motor, cognitive, behavioral, etc – to help control for multiple comparisons) as a result of exercise. Therefore, the data will include the time points immediately pre and post exercise for all subjects. We are interested in both main effects for time and exercise as well as potential interaction effects between exercise group and time.

All subjects completing the protocol and not withdrawing or presenting off study criteria will be included in the analyses. Secondary analyses related to protocol adherence and other aspects of feasibility are anticipated. Estimation of the necessary and sufficient sample size was calculated for a large effect change in the main outcome variable, pre- to post-training change in executive functioning. Significance will be set at p < 0.05.

While we do not anticipate that subjects will improve over time in the absence of exercise, we have included a waitlist control to evaluate this, and we will compare the amount of change over time in the control group versus the exercise group that were not waitlisted using an independent t-test. Also for the exercise group that was not waitlisted, there will be a three month follow up period evaluated to determine whether there is any change compared to the end of the exercise period using paired t-tests.

The change in aerobic capacity and fast elliptical speed will be correlated with changes in the other outcomes measures. Baseline dopamine transmission scores will also be correlated with all motor outcomes using linear regression.

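### For repeated performance tests such as TMT-B, the planned uncontrolled paired t-test from month 3 to month 6 cannot separate retest gain from loss of benefit, and the randomised month-6 comparison that could is not planned

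*Combined protocol and SAP*

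**What the plan says.** Section 9.1 states that "for the exercise group that was not waitlisted, there will be a three month follow up period evaluated", and that the aim is to see "whether there is any change compared to the end of the exercise period using paired t-tests". It gives no comparator, no allowance for retesting, no margin and no interval.

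The other analyses in 9.1 do not fill the gap:

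- The primary model is limited: "the data will include the time points immediately pre and post exercise for all subjects". For the early-exercise arms this leaves out month 6. For the waitlist it uses months 3 and 6.
- The waitlist is compared with the early arms on "the amount of change over time in the control group versus the exercise group that were not waitlisted using an independent t-test". No visit is named, but the stated purpose is to check for change without exercise, and the waitlist is untrained only up to month 3.
- Section 8.2 lists comparisons with the control group without naming a month-6 contrast.

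The design is staggered. Section 4.1 says: "Patients in the control group will then be randomized to either AET or RET, while patients in the exercise training groups will cease" their supervised sessions. All three groups return at month 6, and section 4.4 has every subject with TBI assessed at the same three time points. Section 4.5 allows recent data from related studies to serve as baseline, with the reason: "This is to avoid patient burden and practice effects". Section 4.4.7 says of the early arms after month 3 that "they will be contacted monthly for the next 3 months and asked about their weekly physical activities".

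**The concern.** The paired t-test is the only planned look at what happens after training stops. The primary outcome is a timed test, and month 6 is its third administration. Section 4.5 treats practice effects as real, although it does so when explaining the reuse of baseline data rather than when discussing third testing. The waitlist guards against this kind of change in months 0 to 3. Nothing guards against it in months 3 to 6, because by then no arm is untrained.

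Two misreadings are at stake. A non-significant paired test could be taken as maintained benefit when a loss has been offset by practice. A significant rise could be taken as continued improvement when it is practice alone.

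**Working it through.** **Inputs from the documents.** Significance is set at 0.05 (9.1), taken here as two-sided. Section 9.2 plans 20 subjects per condition, secured to the second assessment visit only, so the two early arms give 20 + 20 = 40 and the waitlist gives 20. Section 9.2 puts attrition at about one-third. The plan states no power or sample size for months 3 to 6, so there is no figure to reproduce.

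**Assumptions, because the documents give no values.** Units are one between-subject SD, with higher meaning better. The between-visit correlation is r = 0.7 to 0.8. The second-to-third retest gain is g = 0 to 0.3. The true loss is L = 0.3 or 0.5.

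**What each analysis estimates.** Let p2 and p3 be the cumulative retest gain at the second and third testing, with g = p3 − p2. Let e be the effect of early training and e′ that of delayed training.

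- Paired change in the early arms: (p3 + e − L) − (p2 + e) = g − L.
- Month-6 difference, early minus waitlist: (p3 + e − L) − (p3 + e′) = −L + (e − e′). This equals −L if e = e′. Retest gain cancels because both groups are at their third testing.
- The waitlist change from month 0 to 3 estimates p2 only, so it cannot be used to subtract g.

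**Size of the problem in the paired test.** The SD of change is √(2(1 − r)), which is 0.775 at r = 0.7 and 0.632 at r = 0.8. With n = 40 the standard error is 0.775/√40 = 0.122 or 0.632/√40 = 0.100. Two-sided rejection rates from the noncentral t are:

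| Net change (absolute value of g − L) | r = 0.7 | r = 0.8 |
|---|---|---|
| 0.0 | 0.05 | 0.05 |
| 0.1 | 0.13 | 0.16 |
| 0.2 | 0.36 | 0.50 |
| 0.3 | 0.67 | 0.83 |
| 0.4 | 0.89 | 0.97 |
| 0.5 | 0.98 | 1.00 |

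- *Spurious further gain (L = 0, so the net change is g).* The rate runs from 13% (g = 0.1, r = 0.7) to 83% (g = 0.3, r = 0.8). If each arm is tested alone (n = 20), g = 0.3 gives 38% at r = 0.7 and 52% at r = 0.8.
- *Masked loss (r = 0.7, n = 40).* Power for a 0.5 SD loss is 0.98, 0.89, 0.67 and 0.36 for g = 0, 0.1, 0.2 and 0.3. For a 0.3 SD loss it is 0.67, 0.36, 0.13 and 0.05. In the last case gain equals loss, and no sample size would reveal the loss.

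**What the month-6 comparison delivers.** In 20,000 simulated trials (40 against 20, r = 0.7, g = 0.1 to 0.3) the estimate stayed within 0.003 SD of the true loss. That simulation assumed e = e′ and no selective dropout. The standard error is s × √(1/n1 + 1/n2), where s = √(2(1 − r)) for change scores and √(1 − r²) with baseline adjustment. If one-third of the waitlist is lost during its training, about 13 remain (20 × 2/3).

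| Early vs waitlist, r | SE, change score | Power, L = 0.3 | SE, adjusted | Power, L = 0.3 |
|---|---|---|---|---|
| 40 vs 20, 0.8 | 0.632 × 0.274 = 0.173 | 0.40 | 0.600 × 0.274 = 0.164 | 0.45 |
| 40 vs 20, 0.7 | 0.775 × 0.274 = 0.212 | 0.29 | 0.714 × 0.274 = 0.196 | 0.34 |
| 40 vs 13, 0.7 | 0.775 × 0.319 = 0.247 | 0.22 | 0.714 × 0.319 = 0.228 | 0.26 |

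The adjusted powers use the normal approximation. With adjustment, at 40 against 20, the loss detectable with 80% power is (1.96 + 0.84) × 0.196 = 0.55 SD at r = 0.7 and 0.46 SD at r = 0.8.

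**The case against.** **Persistence is not a listed objective or outcome.** Section 9.1 asks only whether there is change after training ends, and a paired test answers that within-arm question. This stands. The plan nowhere says that a null result will be called maintained benefit; that is a risk of interpretation.

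**The retest gain may be small.** The documents give no value, and the upper figures need g = 0.3. A reader might infer that the paired test does hide loss. The documents support only that it can.

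**The month-6 comparison is not perfectly clean.** A reader might infer that the groups then differ only in 12 weeks without exercise. The documents do not support that:

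- The early arms stop supervised training but may stay active, which is why their activity is asked about.
- The 30-of-36-session requirement (4.4.7) acts before month 3 in the early arms and after it in the waitlist.
- The analysis set is completers (9.1), and withdrawals are replaced (7.3).
- The waitlist is split between AET and RET. By type, the comparison is about 20 against 10.

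All of this stands as limits on interpretation and shapes the fix.

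**The comparison is imprecise.** This also stands. Without retest gain, the paired test detects a 0.5 SD loss with power 0.98, against 0.64 for the change-score contrast (40 against 20, r = 0.7). A null result from the contrast would not show persistence either.

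**Not every outcome is affected.** No retest argument is offered for peak VO2, MRI or biomarkers. A reader might infer that paired tests should be dropped throughout, but nothing here supports that.

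**Conclusion.** The point holds for TMT-B and the other repeated performance tests. The planned paired test estimates g − L, and nothing in 9.1 separates the two terms. With no true loss, n = 40, g of 0.1 to 0.3 SD and r of 0.7 to 0.8, it reports spurious further improvement in about 13% to 83% of trials. A real loss can be masked to a similar degree. These figures rest on assumed g and r; if g is near zero, the problem disappears.

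A randomised comparison that removes shared retest gain is available from data already collected and is not planned. It estimates loss relative to just-completed training, after supervised exercise stops. It does not estimate benefit over no exercise, nor the effect of 12 weeks without any exercise. Reading it as loss also requires equal efficacy of early and delayed training. The primary TMT-B comparison with the waitlist is unaffected. This is a cheap improvement to what can be concluded about persistence.

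**What to change.** In section 9.1:

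1. For TMT-B and the other performance tests, add a baseline-adjusted month-6 comparison of the pooled early-exercise arms with the waitlist arm. Analyse subjects as randomised, use all randomised subjects with month-6 data, state how missing data are handled, and give a 95% confidence interval.
2. Make this comparison the basis for any statement about persistence. Report the paired change beside it, and state that a non-significant paired result does not show maintained benefit.
3. Keep the paired tests for outcomes without a retest concern, such as peak VO2, MRI measures and biomarkers.
4. State the limits: the estimate is relative to just-completed training, and it assumes equal efficacy of early and delayed training. Describe activity in the early arms after month 3 from the monthly calls.

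**Cost.** There are no new visits or data. The work is wording in 9.1 plus an analysis set and a missing-data rule for this comparison, which differ from the present completer rule. The price is precision: at 40 against 20 and r = 0.8 the standard error is about 0.17 SD, against 0.10 SD for the paired test. On change scores, power for a 0.3 SD loss is 0.40 in that case and 0.22 at 40 against 13 with r = 0.7. The result should be presented as an estimate, not as a test of no loss.

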# Precis

# Objective

The broad objective of this study is to examine the effects of moderate and more intense aerobic exercise as an intervention on cognitive performance, physical functioning and health-related quality of life in patients with chronic (more than 12 months post-injury) traumatic brain injury (TBI). Importantly, structural and biological brain changes will be measured to examine whether functional outcomes are related to exercise-induced adaptations. It is hypothesized that in the chronic phase of persons with TBI, there will be improved: 1) cognitive function, 2) physical fitness and fatigue severity, 3) motor performance and balance, and 4) mood and depressive symptoms, in those that performed the exercise intervention compared to a control group. It is also hypothesized that these functional improvements will be related to exercise intensity, improved cortical connectivity, dopamine transmission gene scores, and blood biomarkers related to neuroand angio-genesis.

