#### Rapid-Resistive Exercise Training (RET)

CNS IRB Protocol Template (2.5.15)

Rapid, reciprocal exercise will be performed using an elliptical trainer, which allows for safe fast speed training. Similar to the previous study (10-CC-0150), this type of training will involve rapid movement and coordination of all four extremities. Emphasis will be placed on increasing speed, however resistance can be increased to keep the level of exercise at a light to moderate intensity. Exercise intensity would not exceed ~ 50% of maximal VO2 (moderate intensity).

The objectives of this study are:

- Primary To evaluate the effects of exercise training intensity on cognitive function in patients with TBI
- Secondary To evaluate the effects of exercise training intensity on balance, physical fitness and quality of life in patients with TBI
- Secondary To evaluate the effects of exercise training intensity on structural and functional changes in the brain of patients with TBI
- Secondary To examine the relationship between cognitive, behavioral, and motor outcomes and brain imaging, biomarker and genetic outcomes or variables
- Secondary To examine structural/functional brain differences, blood biomarkers and a subset of cognitive and self-reported outcomes between patients with TBI and healthy volunteers within the same age range

Since the direct effects of physical exercise are well known, the primary focus here is on the effects of exercise on cognitive function and on brain connectivity. While we anticipate that exercise regardless of intensity will improve cognitive and behavioral outcomes, we anticipate that the effects will be greater for the aerobic training group such that when the results are analyzed separately for each exercise condition, only the aerobic group will demonstrate a significant change in the primary outcome measure. Study outcomes such as brain imaging, blood biomarkers, cognitive performance and selfreported questionnaires in patients with TBI will also be compared to a healthy volunteer sample matched to the TBI cohort for sex and age within 5 years.

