### 9.2 Power analysis

Based on findings in the pilot study (11-CC-0088) [32], calculations indicate that 20 subjects would be needed to detect a significant difference in the main outcome variable of executive functioning with Trail Making Test B for an  $\alpha = 0.05$  and  $\beta=0.05$ . Therefore, 20 subjects in each of the conditions are expected (total 60 subjects). Attrition is approximately one-third for an exercise training protocol, so we predict recruitment of 80 subjects with non-penetrating TBI to have at least 20 subjects in each condition have completed the second assessment visit.

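### Change in fitness and elliptical speed is to be correlated with change in other outcomes with no arm term, so the result can partly restate the group difference

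*Combined protocol and SAP*

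**What the plan says.** Section 9.1 gives the change-change correlations one sentence: "The change in aerobic capacity and fast elliptical speed will be correlated with changes in the other outcomes measures". It does not say whether arm enters, whether the correlation is taken within arms, or which subjects and visits are used. The same section does name exercise group as a factor for the ANOVA, and states for that analysis that "the data will include the time points immediately pre and post exercise for all subjects". It does not say whether that window also governs the correlations. The threshold is general: "Significance will be set at p < 0.05".

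Section 8.2 mentions correlations taken both inside and between arms, but only for baseline measures, so it does not fill the gap.

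The plan expects arm to affect both sides of these correlations:
- The Precis (Design) describes AET as the aerobic stimulus.
- Section 4.4.7 B makes movement speed the main goal of RET.
- Section 2 expects that, with the exercise conditions analysed separately, only AET will show a significant change in the primary outcome.

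On purpose, the Precis expects that "these functional improvements will be related to exercise intensity, improved cortical connectivity, dopamine transmission gene scores", and a secondary objective in section 2 is "To examine the relationship between cognitive, behavioral, and motor outcomes and brain imaging, biomarker and genetic outcomes or variables". Neither sentence names fitness or speed change as the explanatory variable. The Precis does say that functional outcomes are to be related to adaptations induced by exercise.

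**The concern.** A correlation across all subjects combines two things: the association inside each arm, and the association between arm means. If AET raises both peak VO2 and cognitive performance, the arm means alone produce a positive correlation, even if the subjects who gained most in fitness were not those who gained most in cognition. The result then repeats the group comparison, but reads as evidence that individual cognitive gain follows individual fitness gain.

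For elliptical speed the artefact can have the opposite sign. If RET mainly moves speed and AET mainly moves the outcome, the arm means produce a negative correlation, which can hide or reverse a true within-arm association.

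What is at stake is the interpretation of a secondary analysis in a trial that wants to relate functional gains to exercise-induced adaptation.

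**Working it through.** The plan gives no figure for this analysis, so there is none to reproduce. Its sample size is used only to fix the group sizes.

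**Inputs**
- Completers: "20 subjects in each of the conditions are expected (total 60 subjects" (section 9.2).
- Peak VO2 change with aerobic training: +3.1, SD of change 2.4 (Table 1, section 1.2.1). Shift = 3.1/2.4 = 1.29 SD. This comes from 10 patients in one group, trained on a treadmill.
- Outcome shift: assumed 0.5, 0.8 and 1.0 SD. Section 9.1 says "Estimation of the necessary and sufficient sample size was calculated for a large effect change in the main outcome variable" but gives no number.
- Elliptical speed shift in RET: no figure is given; 1.29 SD is assumed.
- Within-arm correlation: zero. Alpha 0.05, two-sided (sidedness is not stated).
- Both changes are coded so that positive means improvement; for raw TMT-B time the sign flips.

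**Formula.** In within-arm SD units, with Bx and By the between-arm variances of the two mean changes and Bxy their between-arm covariance, the correlation induced by arm alone is

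r = Bxy / √[(1 + Bx)(1 + By)].

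**Three arms of 20, only AET moves, outcome shift 0.8.**
- Bx = 1.29² × (1/3)(2/3) = 0.371
- By = 0.8² × 2/9 = 0.142
- Bxy = 1.29 × 0.8 × 2/9 = 0.230
- r = 0.230/√(1.371 × 1.142) = 0.18

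**Exercise periods only, 30 AET and 30 RET, only AET moves, outcome shift 0.8.** This is the set if all 60 exercise, with 20 wait-list subjects split evenly. The factor 2/9 becomes 1/4.
- Bx = 0.417, By = 0.160, Bxy = 0.258
- r = 0.258/√(1.417 × 1.160) = 0.20

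**Elliptical speed, three arms, RET moves speed and AET moves the outcome, shift 0.8.**
- Bxy = −(1.29/3)(0.8/3) = −0.115
- r = −0.115/√(1.371 × 1.142) = −0.09

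**Share of trials with a significant pooled correlation** (20,000 simulated trials per scenario; repeat runs agree to about one percentage point):

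| Scenario | 0.5 SD | 0.8 SD | 1.0 SD |
|---|---|---|---|
| Peak VO2, 3 × 20, only AET moves | 15% | 29% | 41% |
| Peak VO2, 30 AET / 30 RET, only AET moves | 17% | 34% | 48% |
| Peak VO2, 3 × 20, RET moves half as much | 11% | 20% | 27% |
| Peak VO2, 30/30, RET moves half as much | 6% | 7% | 9% |
| Speed, 3 × 20, RET moves speed, AET moves outcome (r negative) | 7% | 11% | 13% |

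In the first row the mean pooled r is 0.12, 0.19 and 0.22. In the speed scenario with exercise arms only (30/30), r is −0.20 and the rate 35% at 0.8 SD. If the outcome shift is zero, the rate is 5%. With arm in the model, the rate is about 5% in every scenario.

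**Cost of adjusting if fitness really acts.** With three arms of 20, VO2 shifted by 1.29 SD in AET only, and the outcome depending on fitness with an assumed slope of 0.3, power is about 75% for the pooled correlation and 60% for the arm-adjusted one.

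**The case against.** The strongest case against the point has four parts.

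1. The plan is silent rather than wrong. It says only that changes will be correlated, and the next sentence uses the same verb for an analysis by linear regression. A reader might infer that a simple pooled correlation has been specified; the text neither states nor excludes that. This stands. The gap still matters, because the choice is otherwise left until the data have been seen.

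2. The largest rates need RET to move neither variable. Section 2 anticipates that exercise at either intensity will help, with AET helping more. With RET at half the AET shift and no untreated arm, the rate is only 6% to 9%. This stands, and the size must be given as a range. Dropping the untreated period is not enough by itself: with RET at zero, the 30/30 set still gives 17% to 48%.

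3. When arm means differ on both variables, the pooled correlation truly is non-zero, so a significant result is not a test error. This stands. The fault would lie in reading the result as an individual-level link.

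4. Arm is the randomised source of variation in fitness. Conditioning on it sets that contrast aside, keeps only observational variation and loses power if fitness mediates. This stands against using the adjusted estimate alone, but not against reporting it.

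**Conclusion.** The point holds as a gap in a secondary analysis. With no arm term, and with arm expected to move both sides, the planned correlation cannot separate a group difference from an association among individuals. The size depends on the assumptions: about 15% to 48% significant if only AET moves both variables, 6% to 27% if RET moves half as much, and no inflation if the arms do not differ on one variable. For elliptical speed the artefact can be negative. The VO2 shift rests on a small uncontrolled pilot, and the outcome and speed shifts are assumptions.

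Three stronger readings are not supported. A reader might infer that the analysis would report a link whenever the arms differ on both variables; even in the three-arm case with only AET moving, 59% to 85% of trials would not. A reader might infer that the pooled correlation should be dropped; it uses the randomised contrast and has more power if fitness mediates. A reader might infer that the trial's main result is at risk; the primary ANOVA already has group as a factor and is unaffected.

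**What to change.** In section 9.1:
- State the analysis set for these correlations: which subjects, which pair of visits, and whether the wait-list control period is included.
- Beside the pooled correlation, report a regression of outcome change on fitness change (or speed change) with arm as a covariate, and show within-arm scatterplots.
- State in advance that any claim that individual gains track fitness or speed gains rests on the arm-adjusted estimate, and that this estimate remains observational and does not by itself establish mechanism.

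The cost is two degrees of freedom with three arms, or one with two. The adjusted estimate has lower power than the pooled correlation if fitness truly mediates the benefit, as in the 60% against 75% example. No new data and no change to trial conduct are needed.

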# 2. Study objectives

The broad objective of this study is to determine the effectiveness of two types of exercise training in patients with non-penetrating TBI for improving cognitive performance, balance, physical fitness, fatigue severity and other behavioral or quality of life outcomes. This study will also measure structural and functional changes in the brain and specific biomarkers known to be involved in brain plasticity as well as to examine genetic factors that may affect responsiveness to the training. This study may also identify the intensity of exercise training that is more highly associated with specific cognitive, functional and structural improvements.

The 2 exercise regimens to be used are as follows:

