# 8. Outcome measures

### 8.1 Primary Outcome

The primary outcome measure for this study is the change in cognitive function as measured by Trail Making Test Part B (TMT-B). This is measured as the difference in the time taken to complete the test between pre and post-exercise intervention and compared to the control group. Standardized t-scores will be used to interpret the results of this test.

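### The only planned dopamine-score analysis covers motor outcomes, leaves level or change unstated and has no score-by-exercise term, so it specifies no test for cognition and cannot separate training response from prognosis

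*Combined protocol and SAP*

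**What the plan says.** The aims that involve the score are broad. The Objective in the Precis lists the expected gains: "there will be improved: 1) cognitive function, 2) physical fitness and fatigue severity, 3) motor performance and balance, and 4) mood and depressive symptoms". It then hypothesizes that "these functional improvements will be related to exercise intensity, improved cortical connectivity, dopamine transmission gene scores", among other factors. Section 2 says the study will "examine genetic factors that may affect responsiveness to the training". One of its secondary objectives is "To examine the relationship between cognitive, behavioral, and motor outcomes and brain imaging, biomarker and genetic outcomes or variables". Section 8.1 makes the primary outcome cognitive: change in TMT-B.

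The analysis is narrow. Section 9.1 has a single sentence on the score: "Baseline dopamine transmission scores will also be correlated with all motor outcomes using linear regression". The sentence just before it, on other predictors, does specify changes: "The change in aerobic capacity and fast elliptical speed will be correlated with changes in the other outcomes measures". The mixed-model ANOVA in section 9.1 has time and exercise group as its only factors, so the score does not enter there either.

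**The concern.** A hypothesis spanning four functional domains is matched by a model for one, and the missing domains include that of the primary outcome. Someone analysing the trial from section 9.1 alone would have no instruction to relate the score to TMT-B.

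The second difficulty concerns the section 2 question about response to training. A regression of an outcome on the score alone describes who does better. It does not show who gains more because of exercise. A patient with a favourable score might perform better at every visit, or improve on retesting with or without training. Separating these requires the unexercised waitlist change. The design supplies that change, but the dopamine sentence does not use it. At stake is whether a secondary finding on genetics can bear the interpretation that section 2 invites.

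**Working it through.** The plan gives no sample size, power or effect size for this analysis, so there is no figure to reproduce. The main check is a comparison of texts.

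**1. Aims against specified models**

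| Domain in the Precis | Model with the dopamine score in section 9.1 |
|---|---|
| Cognitive function (primary outcome domain) | none specified |
| Physical fitness and fatigue | none specified |
| Motor performance and balance | linear regression on the score |
| Mood and depressive symptoms | none specified |

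One domain of four is covered and three are not.

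**2. Level or change**

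The dopamine sentence does not say. Section 8.2 lists the motor secondary outcomes as changes, so a change reading is reasonable. The preceding sentence in section 9.1 names changes and this one does not, so a level reading is also open.

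**3. Comparator**

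Section 9.1 describes its data as the time points just before and just after exercise for all subjects. If those data are used here, the waitlist group contributes its later exercise period and its unexercised 12 weeks drop out. Those weeks do appear in section 9.1, but only in a t-test of change without the score.

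**4. Illustration of what each model detects**

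Every effect size in this step is an assumption. There are 60 patients, 20 waitlist and 40 exercise, matching the planned completers in section 9.2. The score g is standard normal and ex is 1 for exercise, 0 for waitlist.

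- baseline = a·g + e1, with SD(e1) = 1
- change = 0.5·ex + m·g·ex + c·g + e2, with SD(e2) = 0.8
- follow-up = baseline + change

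Tests are two-sided at 0.05 (section 9.1 does not state sidedness), with 4,000 runs per case. The interaction model here was change on g, ex and g·ex, without baseline adjustment.

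| Share of runs significant | Baseline level on g | Follow-up level on g | Change on g | Score-by-exercise term |
|---|---|---|---|---|
| A: score shifts baseline only (a = 0.5) | 96% | 82% | 5% | 5% |
| B: score modifies response only (m = 0.5) | 5% | 47% | 81% | 57% |
| C: score shifts change equally in all arms (c = 0.5) | 5% | 80% | 99% | 5% |

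In A and C the score has no effect on response to exercise. Level regressions fail to make the distinction in A, and the change regression fails in C. Only the interaction stays at 5% in both.

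**5. Precision of the interaction**

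Under the same assumptions (residual SD 0.8, score SD 1), the large-sample standard errors are:

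- pooled exercise against waitlist: 0.8 × √(1/20 + 1/40) = 0.8 × 0.274 = 0.22, so the 95% half-width is 1.96 × 0.22 = 0.43
- one exercise arm against waitlist: 0.8 × √(1/20 + 1/20) = 0.8 × 0.316 = 0.25, so the half-width is 1.96 × 0.25 = 0.49

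Both are about as large as the assumed slope of 0.5. Small-sample intervals would be slightly wider.

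**The case against.** The strongest reply is that the planned regression does what the Precis asks in the motor domain. The Precis speaks only of improvements being related to the score. Section 8.2 frames motor outcomes as changes, and the dopamine sentence follows one about correlating changes. On that reading, regressing motor change on the score is a legitimate test of the stated relation for motor function. This stands. A reader might infer that the plan cannot test its dopamine hypothesis in any domain, and the documents do not support that.

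A reader might also infer a formal hypothesis that training gains depend on genotype. There is none. The wording about responsiveness is a tentative aim in section 2, so the missing interaction is a shortfall against that aim and not against the Precis hypothesis.

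The motor focus has some textual basis. Section 4.4.1 mentions response to motor training and exercise among the reasons for measuring these markers. That may explain the choice, but it does not remove cognition from the hypothesis or the secondary objective.

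Section 8.2 allows further secondary analyses that may correlate baseline measures. This is optional, does not name the score and does not reach response to training, so the gap remains.

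The change regression is also the more sensitive tool when modification is real (81% against 57% in case B). That is true, but case C shows that its positive result is not specific to response.

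Finally, one might infer a large false-positive problem from testing the score against every motor variable. That is a separate matter. Its size depends on correlations among the motor measures, which the documents do not give.

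**Conclusion.** The concern holds in limited form. Section 9.1 specifies a dopamine-score model for one of four hypothesized domains and none for cognition. It leaves open whether the motor outcomes are levels or changes. Even on the favourable reading, it cannot separate response to training from prognosis. The first two statements rest on the text alone. The third follows from the absence of an unexercised comparison. The simulated rates show the mechanism under assumed effects and do not predict what this trial will find.

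The point is minor: it touches a secondary aim and leaves the primary TMT-B analysis unchanged.

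**What to change.** In section 9.1, replace the dopamine sentence with a model of change from baseline to 3 months on dopamine score, exercise and score-by-exercise, adjusted for the baseline value of the outcome. Code exercise as both exercise groups pooled against waitlist, and also show AET and RET separately, since intensity is the study's focus. Fit the model for TMT-B first and then for one motor outcome named in advance. Report the interaction with its 95% confidence interval and label it exploratory.

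For fitness and fatigue and for mood, either add the same model as exploratory or narrow the Precis hypothesis and the secondary objective to the domains that will be analysed.

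The cost is SAP wording and a few regressions on data already planned: genetic testing at baseline and outcomes at baseline and 3 months. The drawback is an imprecise interaction estimate at about 60 completers, more so for AET and RET separately. A null result should therefore not be read as evidence that the score is irrelevant to response.
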